Aim 1. Compare pre-post health insurance status, primary care, mental health, and dental visits, and receipt of preventive services, as well as changes in payer mix among ADVANCE CHCs in states that did and did not expand Medicaid. *Hypothesis 1a:* CHCs in expansion states will experience an increase in overall visits and visits paid by Medicaid, relative to non-expansion states. *Hypothesis 1b:* The percentage of Medicaid visits in CHCs' overall payer mix will increase more significantly in expansion-states relative to non-expansion states.

Aim 2. Examine pre-post utilization of CHC services (including receipt of preventive services) by newly insured compared to already insured and uninsured patients. *Hypothesis 2:* Newly insured patients will have a significant increase in overall CHC visits compared to (a) already insured and (b) uninsured patients.

Aim 3: Measure pre-post changes in overall utilization of healthcare services and Oregon Medicaid expenditures among newly insured compared to already insured patients.

Hypothesis 3a: There will be an increase in utilization of CHC services and a decrease in use of services external to the CHCs (*e.g.*, emergency department) for newly insured patients, but these utilization rates will remain the same for already insured patients. *Hypothesis 3b:* There will be an initial increase, then plateau, in overall Medicaid expenditures among newly insured relative to already insured patients.

Data Sources

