Study Population	OCHIN Medicaid patients within 3 chronic disease cohorts: patients with diabetes (N=608); patients with hypertension patients (N=1244); patients with hyperlipidemia patients (N=546). Patients gained Medicaid coverage between 2008-2011: Patients aged 1-+64 years; Non-pregnant, non-deceased; Uncontrolled biomarker result in EHR within 6 months before/after gained Medicaid coverage.
Exclusion Criteria	Pregnant women
Independent Variables	Insurance status, time, “spline” (slope change at 6 months) interactions between time and insurance and spline and insurance.
Dependent Variables	Biomarkers: 1. HbA1c

	
 2. Systolic blood pressure 3. Diastolic blood pressure 4. Lipids
Covariates	federal poverty level, comorbidities
Analysis Plan	Time to event assessing time from uncontrolled baseline measurement to follow up controlled measurement; Longitudinal analysis modeling the mean biomarker value over time; Logistic regression to estimate the odds of having a disease-specific medication ordered during study.
Data Set Name	PPDA Projects → PACE → CARDIACBiomarker → Data → all the files in there Code is under: PPDA Projects → PACE → CARDIACBiomarker → Rcode
Code Location	Box at OHSU

Uninsured Primary Care Visit Disparities Under the Affordable Care Act

Full Citation	Angier, H., M. Hoopes, M. Marino, N. [name], E. A. Jacobs, J. [name], H. Holderness, C. M. Hood and J. E. DeVoe (2017). Uninsured Primary Care Visit Disparities Under the Affordable Care Act. Ann Fam Med 15 (5): 434-442.
Objective	To assess changes in insurance coverage at community health center (CHC) visits after the Patient Protection and Affordable Care Act (ACA) Medicaid expansion by race and ethnicity
Study Population	
 1. N=870,319 2. 359 CHCs 3. CHC patients aged 19-64 years 4. Expansion states as of 1-1-14: California, 5. Hawaii, Maryland, Minnesota, New Mexico, Ohio, Oregon, Rhode Island, Washington, and Wisconsin 6. Non-expansion states as of 1-1-14: Florida, Kansas, Missouri, North Carolina, Texas, Montana
Exclusion Criteria	Pregnant women
Independent Variables	Expansion status (Medicaid expansion vs. non-expansion)
Dependent Variables	Health insurance type at each visit (Medicaid-insured, uninsured, privately-insured)
Covariates	
Analysis Plan	
 1. Difference-in-difference (DID) 2. Difference-in-difference-in-difference (DDD) 3. GEE models

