Covariates	Age, sex, language, race/ethnicity, federal poverty level, and clinic location
Analysis Plan	1. Adjusted predicted probability 2. Mixed effects ordinal logistic regression 3. Random effects to account for clustering visits
Data Set Name	PAT_CONSORT_08312016 encounters_AV1215_pipe FAC_URBRUR STATES PPDA_RUCA_CHARLSON PPDA_PREEXISTING_CONDITIONS Code is under: PPDA Projects -> Who_Remains_Uninsured -> draft4.Rmd
Code Location	Box at OHSU

Utilization of Community Health Centers in Medicaid Expansion and Non-expansion States, 2013-2014.

Full Citation	Hoopes, M. J., H. Angier, R. Gold, S. R. Bailey, N. [name], M. Marino and J. E. DeVoe (2016). Utilization of Community Health Centers in Medicaid Expansion and Non-expansion States, 2013-2014. J Ambul Care Manage 39(4): 290-298.
Objective	Assess CHC utilization a full year before and after the implementation of Affordable Care Act (ACA) Medicaid expansions (24 months) and describes changes in visit type before and after implementation.
Study Population	Adults 19-64 years, billed visits in pre expansion (1/1/13-12/31/13) and post expansion (1/1/14-12/31/14) OCHIN member clinics. N=401,988 patients.
Exclusion Criteria	Pregnant women
Independent Variables	Expansion status
Dependent Variables	1. Insurance status 2. Visit type
Covariates	Sex, age, race/ethnicity, urban/rural, federal poverty level, minimum wage, unemployment, insurance exchange type.
Analysis Plan	1. GEE 2. Poisson models
Data Set Name	OCHIN: e:\sasroot\CATCHUP\ACA 12 month
Code Location	OCHIN SAS server

Effect of Gaining Insurance Coverage on Smoking Cessation in Community Health Centers: A Cohort Study.

Full Citation	Bailey, S. R., M. J. Hoopes, M. Marino, J. [name], J. P. O'Malley, B. Hatch, H. Angier, S. P. Fortmann and J. E. DeVoe (2016). Effect of Gaining Insurance Coverage on Smoking Cessation in Community Health Centers: A Cohort Study. J Gen Intern Med 31(10): 1198-1205.
Objective	To determine if uninsured community health center (CHC) patients who gained Medicaid coverage experienced greater primary care utilization, receive more cessation medication orders, and achieve higher quit rates, compared to continuously uninsured smokers.
Study Population	CHC patients aged 19–64 years who gained Oregon Medicaid coverage between 2008 and 2011 after being uninsured for ≥ 6 months and who maintained this insurance for ≥ 6 months. Cohort of ‘current every day smoker’ or ‘current some day smoker.’

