Exclusion Criteria	Non-smoking, pregnant, non-living, private insurance, Medicare insurance.
Independent Variables	Insurance Status
Dependent Variables	1. 'Quit' smoking status (yes/no) 2. Smoking cessation medication ordered (yes/no)
Covariates	Usual source of care after in follow up period.
Analysis Plan	1. Propensity score matching 2. Between group differences 3. GEE for clustering
Data Set Name	Smoking_model_set_PSmatches.sas7bdat
Code Location	OCHIN archive server

Observational Study of Racial/Ethnic Disparities in Health Insurance and Differences in Visit Type for a Population of Patients with Diabetes after Medicaid Expansion.

Full Citation	Angier, H., D. Ezekiel-Herrera, M. Marino, M. Hoopes, E. A. Jacobs, J. E. DeVoe and N. [name] (In press). Observational Study of Racial/Ethnic Disparities in Health Insurance and Differences in Visit Type for a Population of Patients with Diabetes after Medicaid Expansion. J Health Care Poor Underserved.
Objective	To understand the impact of the Affordable Care Act (ACA) Medicaid expansion on racial/ethnic health insurance disparities and differences in visit type for a population of patients with diabetes, by assessing changes pre- versus post-ACA in expansion compared with non-expansion states.
Study Population	Adults aged 19-64, diabetes diagnosis any time during study period, CHCs in ADVANCE network with EHRs live as of January 2013.
Exclusion Criteria	Pregnant women
Independent Variables	Expansion status
Dependent Variables	1. Health insurance status 2. Healthcare visit types a. Total b. Type
Covariates	Sex, age, FPL, Charlson comorbidity index score, state-level factors
Analysis Plan	1. Incidence rates 2. GEE Poisson models 3. Difference in Difference

Data Set Name	Analytic Data: PPDA Projects → PACE → Diabetes Disparities → Analytic Data Code: PPDA Projects → PACE → Diabetes Disparities → Code
Code Location	Box at OHSU

Assessing the prevalence of pre-existing conditions among community health center patients.

Full Citation	[name], N., H. Angier, M. J. Hoopes, M. Marino, J. [name], T. Schmidt and J. E. DeVoe. Assessing the prevalence of pre-existing conditions among community health center patients. Medical Care. Submitted 9/18
Objective	To assess the prevalence of pre-existing conditions pre- versus post-Affordable Care Act (ACA) for community health center (CHC) patients who gained insurance

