Secondary data analysis will be conducted.

7) Data and Specimens

a) Sharing of Results with Subjects

Results will not be directly shared with subjects.

b) Data and Specimen Banking

No specimens are being collected. Data is not being banked for future research.

8) Data Analysis

We will summarize baseline measures using descriptive statistics and data visualization methods (*e.g.*, histograms, scatter plots) to characterize baseline data across clinic and state groups. We will estimate the differences in access and receipt of recommended health care. We will also assess health care expenditures. Our primary methodological approach will utilize difference-in-differences (DID) methodology. The DID approach has been frequently used by health economists and health services researchers to account for potential secular effects and changing policies that would affect both expansion and non-expansion states over time, while adjusting for potential confounders.¹¹⁻¹⁶

We will implement state random effects in clinic-level analyses and both clinic and state random effects in patient-level analyses to control for correlation of observations nested in clusters (*e.g.*, individuals nested in clinics which are nested in states). We recognize that the assumption for random effects may not be met and we will also assess the robustness of our

assumptions by running models that treat clinics and states as fixed effects. We will formally test the validity of the random effects using the standard Hausman test,¹⁷ as well as assessing overall qualitative differences that may arise between the random and fixed effects models.

We will use GLMM models,¹⁸ which offer flexible regression modeling to accommodate different sources of correlations (serial, intra-clinic, and intra-state), categorical and continuous covariates, and fixed and time-dependent covariates. These methods offer a wide range of parametric distributions to model the dependent variables, including logistic regression (binary data), beta regression (percent data), Poisson regression (count data), and Gaussian regression (normally distributed data). The distribution of the outcomes of interest will be examined before selecting an analysis model; specific models will be refined through an iterative process.

Potential variables included in the analyses	Description
Age	Categories
Sex	Male/female, other
Race	White, American Indian/Alaskan Native, Asian, Black, Native Hawaiian/Pacific Islander, Other

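### The biomarker study's time-to-control result depends on how often patients are measured; if patients gaining Medicaid are measured more often, they will seem to reach control sooner with an identical biomarker course

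*Combined protocol and SAP*

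**What the plan says.** The point concerns the chronic disease biomarker study, one of the sub-study tables under Data Analyses in the combined protocol and SAP. Its patients gained Oregon Medicaid coverage in 2008–2011.

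- **Entry:** "Uncontrolled biomarker result in EHR within 6 months before/after gained Medicaid coverage".
- **Control analysis:** "Time to event assessing time from uncontrolled baseline measurement to follow up controlled measurement".
- **Other analyses in the same table:** a longitudinal model of the mean biomarker value, and a logistic model for medication orders. None of the three is named as primary.
- **Independent variables:** "Insurance status, time, “spline” (slope change at 6 months) interactions between time and insurance and spline and insurance". The table does not describe the comparison group.
- **Covariates:** "federal poverty level, comorbidities", and nothing else.
- **Source of readings:** the IRB protocol's Procedures section states "Secondary data analysis will be conducted", so readings occur when patients attend and not on a study schedule.

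The table gives no assessment window, no rule for readings taken at unequal intervals, and no adjustment or weighting for measurement frequency. Hypothesis 2 of the project, under Aim 2, is that "Newly insured patients will have a significant increase in overall CHC visits compared to (a) already insured and (b) uninsured patients".

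**The concern.** A patient can be recorded as controlled only on a day when a reading is taken. More frequent readings act in two ways. They date a real crossing of the threshold earlier. For a biomarker that varies from reading to reading, they also give more chances of a single low value. Both effects shorten the recorded time to control without any change in the patient.

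If gaining coverage brings more visits, measurement frequency is a consequence of the exposure being studied. The hazard ratio then mixes better disease control with closer observation, and a finding that Medicaid speeds control could arise with no biological difference at all.

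**Working it through.** **What the documents supply.** They give cohort sizes of 608 (diabetes), 1,244 (hypertension) and 546 (hyperlipidemia). They give no reading rates, event counts or hazard ratio for this study, so there is no stated figure to reproduce. Reading rates, follow-up (24 months) and biomarker distributions below are assumptions. The true hazard ratio is 1 throughout, and readings arrive at random (Poisson) times.

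**Step 1: no reading error, delayed detection only.** Let true time to lasting control be exponential with rate λ, and let readings occur at rate r per year. The wait from true control to the next reading averages 12/r months: 6 months at r = 2, 4 at r = 3, and 3 at r = 4. The recorded time to control has survival function

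S(t) = [r·exp(−λt) − λ·exp(−rt)] / (r − λ).

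With a true median of 12 months, λ = ln 2 = 0.693 per year. Setting r = 2 and t = 1.55 years gives (2 × 0.342 − 0.693 × 0.045)/1.307 = 0.50, an apparent median of about 18.6 months. The same formula gives 16.4 months at r = 3 and 15.2 at r = 4. Simulation agrees, and a Cox model on the simulated data gives:

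| Readings per year | HR, true median 6 months | HR, true median 12 months |
|---|---|---|
| 3 vs 3 | 1.01 | 1.00 |
| 3 vs 2 | 1.25 | 1.15 |
| 4 vs 2 | 1.38 | 1.25 |

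**Step 2: stable biomarker, reading noise only.** If a person's chance of a controlled value at any reading is p, the event rate is r·p. For that person, the ratio between two reading rates is exactly r₁/r₀: 3/2 = 1.5 or 4/2 = 2.0. Differences in p between people pull the Cox estimate below these values.

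- Systolic cut-off 140, usual values N(142, 8), within-person SD 10, entry on one uncontrolled reading: HR 1.39 at 3 vs 2 and 1.67 at 4 vs 2. Repeat runs gave 1.35 to 1.38 and 1.69 to 1.70. Equal rates gave 0.99.
- Level N(0.8, 0.8) above the threshold in arbitrary units, reading SD 0.7: 1.33 and 1.63.
- Less noise (mean 148, between-person SD 12, within-person SD 6): 1.27 at 3 vs 2.

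**Step 3: effect on the test.** Use Step 1 with a 12-month median, and assume that each stated cohort size is a total split 1:1. The rejection rate at nominal 5% is then 30% to 59% at 3 vs 2 readings a year and 60% to 92% at 4 vs 2. With equal rates it is 3.5% to 6.5%.

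**Step 4: alternatives, tested with no true difference.**

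- *Status at the reading nearest 12 months:* 32% to 34% controlled in every arm of the systolic simulation, so the spurious difference disappears.
- *Interval-censored analysis:* HR 0.98 to 1.01 in Step 1, where there is no reading noise.
- *Two consecutive controlled readings:* Cox HRs of 1.49 to 1.55 (3 vs 2) and 1.86 to 1.98 (4 vs 2). An interval-censored version gave 1.41 and 1.61. Requiring confirmation does not remove the bias.

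**The case against.** **The table is a short summary of a published paper.** It does not print the word first or name a Cox model, and the paper or code may hold rules not shown here. That stands as a limit on what can be said about the analysis actually run. Still, the first qualifying reading is the ordinary meaning of a time-to-event endpoint, and the table offers no other rule.

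**Unequal measurement is not documented.** A reader might infer that the project has established, or at least predicts, more readings in this cohort. It does neither. Hypothesis 2 is about overall visits in the main project, whose pre-period is 2013, not about HbA1c, blood pressure or lipid readings in a 2008–2011 cohort. The smoking cessation study, from the same years in Oregon, asks whether patients gaining Medicaid "experienced greater primary care utilization, receive more cessation medication orders". That is a question and not an expectation. Unequal measurement is therefore plausible only.

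**The larger simulated ratios come from unfavourable settings.** In Step 2 every control event is noise. This is fair, and it is why a range is given that includes the noise-free case. HbA1c was not simulated separately.

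**Other safeguards exist.** The SAP's weights for post-period non-users (B.4.4) are a sensitivity analysis for utilization. Its missing-data provisions (B.4.6) concern attrition and missing services. Neither deals with when readings are taken. The longitudinal mean model does not stop at a controlled reading and is a useful cross-check, but it does not correct the hazard ratio.

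**The smoking study.** A reader might extend the point to its quit outcome. The documents do not support that. The outcome is yes/no, no time-to-event analysis is planned, and the table does not say how repeated records are handled.

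**Conclusion.** The concern holds conditionally. As described, the time-to-control analysis gives a biased hazard ratio whenever reading rates differ between insurance groups, in favour of the group measured more often. With equal rates there is no bias. At the assumed rates the spurious hazard ratio is about 1.15 to 1.4 (2 vs 3 readings a year) or 1.25 to 1.7 (2 vs 4), depending mainly on within-person noise. The size in this study cannot be known from the documents, because they give no reading rates by group and no comparator. It would be wrong to conclude that the study's result is an artefact. What follows is that the hazard ratio alone cannot separate better control from more measurement. The change is worth making because one of the three listed analyses could otherwise support a claim of faster control with no biomarker difference behind it.

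**What to change.** 1. Report readings per patient-year by insurance group for each biomarker. If the rates are equal, the concern closes.
2. Make the main control result the status at the reading nearest a fixed time, for example 12 months with a window of ±6 months. Count from an index date defined the same way in both groups, for example the uncontrolled baseline reading. Coverage start does not serve, because a comparator who never gains coverage has no such date.
3. Weight by the inverse probability of having a reading in that window. This assumes that, given the variables in the weights, having a reading is unrelated to the biomarker value. The simulation satisfies this by construction; real visits may not, so the weight model should be stated.
4. If the time-to-control hazard ratio is kept, label it as also reflecting measurement frequency. Do not present it as evidence of better control unless the fixed-time result and the longitudinal mean model agree with it.

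**Cost.** This is a re-analysis of data and code that the table lists as archived. Precision falls slightly, because patients with no reading in the 12-month-wide window contribute only through the weights. With Poisson readings that share is exp(−r): 13.5% at 2 a year, 5.0% at 3, and 1.8% at 4.

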OCHIN and HCN	DUA	Allows OCHIN to share HCN data found in the ADVANCE CDM with OCHIN as a limited data set	6-3-16
OCHIN and OHSU	DUA	Adds Community Vital Signs data to original DUA	5-22-17
OCHIN and Oregon	DAA	Allows OCHIN to use state-owned Medicaid data	6-20-16

See Appendix 3 for full agreements.

Table 4. Decision Log

Study	Influence	Date of Decision	Decision Context	Decision
PACE	Insurance Validation Paper ([name])	03/29/16	PPD Meeting	Will exclude Medicare/Medicaid dual eligibles (since we cannot determine who they are in the ADVANCE data).
PACE	Insurance Validation Paper ([name])	03/29/16	PPD Meeting	Will exclude visits coded as being paid by another public payor – these don't provide information about Medicaid coverage.
PACE	Data Methods	01/12/16	PPD Meeting	Data Pull will include all states, however down the road if there are complications based on a state's data they will be excluded.
PACE	Bio Marker Paper ([name])	02/23/16	PPD Meeting	Analysts will use Oregon Medicaid administrative data to create insurance cohorts to validate ADVANCE visit based insurance groups.
PPD	Definitions	03/15/16	PPD Meeting	Patient state and clinic state will be given, classified as expansion vs non expansion. Patient state will be state at the patient's most recent encounter, not historical state at date of encounter.
PPD	Data Methods	03/25/16	Journal Club	Currently, the methods used within the "Propensity score weighting with multilevel data" article by Li, Zaslavsky and Landrum will be applied to all papers.
PPD	Data Methods	04/01/16	[name]/ [name]/ [name]	Base data pull: Clinic inclusion criteria OCHIN: dept type=primary care, public health, or medical specialty specified as internal med, peds, or women's health. School-based health centers (SBHCs) included. Health Choice network: site type=CHC, peds, SBHC, or hospital specified as outpatient clinic. Exclude based on facility names including radiology, mental, behavioral, substance, dental, pharmacy, or lab. Facility type categorized into: primary care, public health, pediatrics, women's health, mobile, specialty, and SBHC.

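### The biomarker time-to-control analysis omits the qualifying biomarker value, a strong predictor of crossing back to controlled; this costs precision and leaves the insurance comparison exposed to differences in baseline severity

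*Combined protocol and SAP*

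**What the plan says.** The entry is in the Combined protocol and SAP, Data Analyses, under *Medicaid's Impact on Chronic Disease Biomarkers*.

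- **Entry (Study Population row).** Patients need an "Uncontrolled biomarker result in EHR within 6 months before/after gained Medicaid coverage". The cohorts number 608 (diabetes), 1,244 (hypertension) and 546 (hyperlipidemia).
- **Event (Analysis Plan row).** "Time to event assessing time from uncontrolled baseline measurement to follow up controlled measurement".
- **Covariates row.** "federal poverty level, comorbidities", and nothing else.
- **Comparison (Independent Variables row).** Insurance status, time, a slope change at 6 months, and "interactions between time and insurance and spline and insurance". The analysis is therefore comparative, although the population row describes only patients who gained Medicaid.
- **Second biomarker analysis.** "Longitudinal analysis modeling the mean biomarker value over time".

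Two lines of the Decision Log (Table 4) also bear on this. For this paper, "Analysts will use Oregon Medicaid administrative data to create insurance cohorts". A general decision of 03/25/16 says that a published approach to propensity score weighting with multilevel data "will be applied to all papers", but it names no variables for the score.

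The documents do not define controlled or uncontrolled. They give no cut-off, no number of qualifying readings, no confirmation rule and no reading schedule, and nowhere do they list the baseline biomarker value as an adjustment variable.

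**The concern.** Patients are selected because a reading was on the wrong side of a limit, and success is a later reading on the right side. Readings vary within a patient, so some who qualify will cross back with no change in their underlying level. The chance depends heavily on how far out the qualifying value was, and that value is not among the covariates.

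Three things are at stake:

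- **Precision.** A strong predictor of the event is left unexplained.
- **Bias.** Insurance groups are not randomised. If one group starts with milder disease, it reaches control sooner whatever Medicaid does.
- **Interpretation.** Absolute control rates include crossings that are only measurement variation, so they cannot be read as improvement under Medicaid.

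**Working it through.** The documents state no power, effect size, event count, cut-off or variability for this paper, so there is no figure of theirs to reproduce. Everything below is illustrative.

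**Assumed inputs (none from the documents).** Systolic pressure cut-off 140 mmHg; population mean 130–140; between-patient SD 14; within-patient SD 6–12; up to three follow-up readings; no true change unless stated; one qualifying reading, with the same cut-off for entry and event.

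**Step 1. Crossing back with no true change.** Let r be the correlation of two readings in one patient, c the standardised cut-off and q = Φ(c). Then

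P(next reading controlled | entry uncontrolled) = [q − Φ₂(c, c; r)] / (1 − q).

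- Low end, mean 140, within-SD 6: r = 196/(196 + 36) = 0.845 and q = 0.5. The formula reduces to 0.5 − arcsin(0.845)/π = 0.18.
- High end, mean 130, within-SD 12: r = 196/(196 + 144) = 0.576, c = 10/√340 = 0.542 and q = 0.706. (0.706 − 0.576)/0.294 = 0.44.

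The range is 18–44% at the next reading. Simulation gives the same, and 33–71% within three readings. For scale, 0.18 × 1,244 = 224 and 0.44 × 1,244 = 547 patients. Assumed HbA1c inputs (cut-off 8.0, mean 7.5–8.0, between-SD 1.6, within-SD 0.3–0.8) give 8–25% at the next reading.

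**Step 2. How strongly the qualifying value predicts this.** With mean 135 and within-SD 10, no-change control at the next reading is 50% for a qualifying value of 140–145 and 12% for 160–180.

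**Step 3. Equal groups.** With the same true-value distribution and the same number of readings, the ratio of cumulative hazards, log(1 − p₁)/log(1 − p₀), is 1.0 with no effect. It moves if reading frequency differs: 3 against 2 readings gives about 1.25–1.32 (r from 0.9 to 0.5, cut-off at the median).

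**Step 4. Unequal groups, no Medicaid effect.** Same model as step 2, underlying means 4–8 mmHg apart:

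| Model | Null ratio |
|---|---|
| Unadjusted | 1.19 to 1.40 |
| Adjusted for qualifying value | 1.13 to 1.27 |

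Share of the excess removed: (1.19 − 1.13)/0.19 = 0.32 and (1.40 − 1.27)/0.40 = 0.33, about a third. Adjustment is partial because one noisy reading measures underlying severity imperfectly.

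**Step 5. Precision.** For a true 5 mmHg fall and an assumed 622 per group (half of 1,244; the split is not given), adjustment raises the mean z from 5.2 to 5.7. Since (5.7/5.2)² = 1.20, this is worth about 20% more patients.

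**Step 6. Does requiring confirmation recover a diluted effect?** Same 5 mmHg fall, three readings:

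| Event rule | No fall | Fall | Difference | Ratio |
|---|---|---|---|---|
| Any controlled reading | 57.4% | 71.9% | 14.5 points | log(0.281)/log(0.426) = 1.49 |
| Two consecutive | 24.5% | 38.7% | 14.2 points | log(0.613)/log(0.755) = 1.74 |

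Approximate z with 622 per group is ln(ratio)/√(1/events₁ + 1/events₀). Any reading: 0.399/√(1/447 + 1/357) = 5.6. Confirmed: 0.554/√(1/241 + 1/152) = 5.3. The larger ratio is mostly a matter of scale; sensitivity does not improve.

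**Step 7. Longitudinal model.** The expected no-change drop after a qualifying value b is (1 − r)(b − mean). With mean 135 and within-SD 10, 1 − r = 100/296 = 0.338, so b = 150 gives 0.338 × 15 = 5.1 mmHg. If the qualifying reading is the first outcome point, this drop falls in the segment before the 6-month slope change. The insurance interactions cancel it only if the groups start alike.

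**The case against.** The strongest reply is that the question is comparative, and regression to the mean shared by similar groups leaves the null ratio at 1.0. That is correct (step 3). Bias needs an imbalance, and the small gap seen in qualifying values understates how large: in these simulations, gaps of 1.3 and 2.0 mmHg in mean qualifying value needed gaps of 4 and 6 mmHg in underlying mean. No document shows that such an imbalance exists.

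Second, the entry is a short summary of a published paper. The Decision Log keeps detailed criteria in a manuscript tracker and data dictionaries, and the code is archived elsewhere. A reader might infer that entry rests on exactly one reading, that the event is the first controlled reading, or that both use the same cut-off. These come only from singular nouns in table cells; the documents leave the rule undefined.

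Third, propensity weighting was decided for all papers. It could balance baseline severity, but its variables are unlisted and this entry does not mention weighting, so it does not settle the matter.

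Fourth, the qualifying reading may fall up to 6 months after coverage starts. Adjusting for a reading taken after exposure could remove part of the effect. This stands, and it shapes the fix.

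What remains is that the listed covariates omit a strong predictor which the study already holds.

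**Conclusion.** The concern holds in a limited form. Leaving out the baseline value costs precision (about 20% in effective sample size under the step 5 assumptions). It biases the insurance comparison if the groups differ in baseline severity (null ratio 1.19–1.40 for underlying means 4–8 mmHg apart). Absolute control rates are inflated in every group, illustratively by 18–44% of systolic pressure patients at the next reading. All sizes rest on assumed cut-offs, variability and reading rules.

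Two stronger readings are not supported. One is that noise crossings dilute a true Medicaid effect and confirmation would recover it: step 6 shows nearly equal risk differences and no gain in z. The other is that the longitudinal mean must be the main evidence: the documents name no main analysis for this paper, and that model starts from the same selected patients.

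**What to change.** 1. Add the baseline biomarker value, as a continuous covariate, to the time-to-control model. Use a reading taken before coverage began, or restrict to (or report separately) patients whose qualifying reading precedes coverage, so that a post-exposure value is not adjusted away.
2. In the longitudinal model, condition on the qualifying reading or leave it out of the outcome series.
3. Report control confirmed at the next reading as a sensitivity analysis only.
4. Do not interpret absolute control rates as a Medicaid effect.

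**Cost.** One covariate from data already held, and a rerun of archived code. Restricting to pre-coverage readings reduces numbers, and the confirmed endpoint has fewer events and needs a second reading. Adjustment removes only about a third of the excess ratio in the simulation, so residual imbalance in severity should be acknowledged.
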